6.6.5 Visit 06, Day 29, Clinic Visit

(Window: Day 29±3 days post 1st study vaccination)

In addition to the study procedures listed in [Section 6.6](#), the following study procedures will also be performed:

- Approximately 72 mL of venous blood will be collected for cellular immunology assays.
- Approximately 20 mL of venous blood will be collected for antibody assays.
- All AEs/SAEs/AESIs including PIMMCs/MAAEs/NOCMCs will be recorded on the appropriate DCF.

6.6.6 Visit 07, Day 57, Clinic Visit, 2nd Study Vaccination (Dose 2)

(Window: Day 57±3 days post 1st study vaccination)

In addition to the study procedures listed in [Section 6.6](#), the following study procedures will also be performed:

- Eligibility criteria will be reviewed with subjects prior to the second study vaccination to ensure continued eligibility.

- A urine or serum pregnancy test will be performed locally by the site within 24 hours prior to the second study vaccination for all women of childbearing potential. Results must be negative and known prior to the second study vaccination.
- Nasal swab will be collected for SARS-CoV-2 PCR prior to the second vaccination.
- Approximately 2 mL of venous blood will be collected for SARS-CoV-2 serology (N-specific).
- Approximately 14 mL of venous blood will be collected immediately prior to the second study vaccination for baseline clinical safety labs (WBC, HgB, PLT, ALT, AST, ALP, T Bili, CK, and Cr) to be performed by the local (clinical) laboratory. The results from these evaluations will not be available or reviewed prior to the second study vaccination.
- Approximately 72 mL of venous blood will be collected immediately prior to the second study vaccination for cellular immunology assays.
- Approximately 20 mL of venous blood will be collected immediately prior to the second study vaccination for antibody assays.
- Approximately 24 mL of venous blood will be collected for PBMC and plasma storage for secondary research.
- Approximately 2.5 mL of venous blood will be collected for identification of transcriptomal signatures associated with vaccine reactogenicity and immunogenicity.
- Approximately 4 mL of blood will be collected for cytokines.
- Subjects will then receive one- 0.25 or 0.5 mL dose of study vaccine (depending on treatment assignment) via a single IM injection into the deltoid muscle. If possible, administer study vaccine in the opposite arm used for the first study vaccination. The site of injection (right or left arm) and time of study vaccine administration to the subject will be recorded on the appropriate DCF. Subjects will be observed in the clinic for at least 45 minutes after the second study vaccination. The second study vaccination site will be examined, post-administration reactogenicity assessments will be performed, and any AEs/SAEs/AESIs including PIMMCs/MAAEs/NOCMCs will be recorded on the appropriate DCF prior to discharge from the clinic.
- Subjects will be provided with a Memory Aid and other study-related materials to record daily oral temperature, solicited injection site and systemic reactions, unsolicited AEs, and concomitant medications. Subjects will be encouraged to take their oral temperature around the same time each day. Subjects must not eat or drink anything hot or cold within

10 minutes prior to taking oral temperature. Subjects will be instructed on how to use their Memory Aid and how to measure and record AEs prior to discharge from the clinic. Subjects will be instructed to notify the study center if they develop any severe reactions after the second study vaccination. If the site PI or appropriate sub-investigator deems the reaction severe enough, further instructions will be given to the subject on the proper course of action, including a return to the clinic for immediate evaluation if appropriate.

6.6.7 Visit 08, Day 58, Clinic Visit

(Window: Day 2+1 day post 2nd study vaccination)

In addition to the study procedures listed in [Section 6.6](#), the following study procedures will also be performed:

- Memory Aid information will be reviewed with subjects.
- Approximately 2.5 mL of venous blood will be collected for identification of transcriptomal signatures associated with vaccine reactogenicity and immunogenicity.
- Approximately 4 mL of blood will be collected for cytokines.
- All AEs/SAEs/AESIs including PIMMCs/MAAEs/NOCMCs will be recorded on the appropriate DCF.

6.6.8 Visit 09, Day 60, Telephone, Email, or Text Contact

(Window: Day 4+2 days post 2nd study vaccination)

- Memory Aids will be reviewed with the subjects via telephone, email, or text for any AEs (solicited injection site and systemic reactions, as well as unsolicited AEs), SAEs, AESIs, and concomitant medications. Based on the information collected, subjects may be asked to return to the clinic for an evaluation.

6.6.9 Visit 10, Day 64, Clinic Visit

(Window: Day 8+2 days post 2nd study vaccination)

In addition to the study procedures listed in [Section 6.6](#), the following study procedures will also be performed:

- A saliva sample will be collected to check for antibodies.
- Memory Aid information will be reviewed with subjects.

- Approximately 14 mL of venous blood will be collected for safety labs including WBC, HgB, PLT, ALT, AST, ALP, Cr, CK and T Bili
- Approximately 2.5 mL of venous blood will be collected for identification of transcriptomal signatures associated with vaccine reactogenicity and immunogenicity.
- Approximately 4 mL of blood will be collected for cytokines.
- All AEs/SAEs/AESIs including PIMMCs/MAAEs/NOCMCs will be recorded on the appropriate DCF.

6.6.10 Visit 11, Day 71, Clinic Visit

(Window: Day 15+2 days post 2nd study vaccination)

In addition to the study procedures listed in [Section 6.6](#), the following study procedures will also be performed:

- Approximately 72 mL of venous blood will be collected immediately prior to the second study vaccination for cellular immunology assays.
- Approximately 20 mL of venous blood will be collected immediately prior to the second study vaccination for antibody assays.
- Approximately 32 mL of venous blood will be collected for PBMC and plasma storage for secondary research.
- All AEs/SAEs/AESIs including PIMMCs/MAAEs/NOCMCs will be recorded on the appropriate DCF.

6.6.11 Visit 11A, Day 15, Optional Leukapheresis

(Window: Day 15+4 weeks after 2nd study vaccination)

In addition to the study procedures listed in [Section 6.6](#), the following study procedures will also be performed:

- Subjects will be provided with a description of the Leukapheresis substudy (purpose and study procedures) and asked to read and sign the ICF prior to performing the procedure. A Leukapheresis specific informed consent may be needed prior to performing the procedure based on institutional requirements.
- Review eligibility criteria for leukapheresis procedure.
- Blood collection for safety labs required prior to the procedure.

- Urine or serum pregnancy test prior to the procedure.
- Only SAEs that occur during or within 24 hours after the leukapheresis study visit will be recorded on the appropriate DCF.

6.6.12 Visit 12, Day 85, Clinic Visit

(Window: Day 29±3 days post 2nd study vaccination)

In addition to the study procedures listed in [Section 6.6](#), the following study procedures will also be performed:

- Approximately 72 mL of venous blood will be collected for cellular immunology assays.
- Approximately 20 mL of venous blood will be collected for antibody assays.
- Approximately 32 mL of venous blood will be collected for PBMC and plasma storage for secondary research.
- All AEs/SAEs/AESIs including PIMMCs/MAAEs/NOCMCs will be recorded on the appropriate DCF.

6.6.13 Visit 13, Day 141, Clinic Visit

(Window: Day 85±3 days post 2nd study vaccination)

In addition to the study procedures listed in [Section 6.6](#), the following study procedures will also be performed:

- Approximately 72 mL of venous blood will be collected for cellular immunology assays.
- Approximately 20 mL of venous blood will be collected for antibody assays.
- Approximately 32 mL of venous blood will be collected for PBMC and plasma storage for secondary research.
- All SAEs/AESIs including PIMMCs/MAAEs/NOCMCs will be recorded on the appropriate DCF.

6.6.14 Visit 14, Day 237, Clinic Visit

(Window: Day 181±14 days post 2nd study vaccination)

In addition to the study procedures listed in [Section 6.6](#), the following study procedures will also be performed:

- Approximately 72 mL of venous blood will be collected for cellular immunology assays.
- Approximately 20 mL of venous blood will be collected for antibody assays.
- Approximately 32 mL of venous blood will be collected for PBMC and plasma storage for secondary research.
- All SAEs/AESIs including PIMMCs/MAAEs/NOCMCs will be recorded on the appropriate DCF.

6.6.15 Visit 15, Day 422, Clinic Visit, Final Study Visit

(Window: Day 366±14 days post 2nd study vaccination)

In addition to the study procedures listed in [Section 6.6](#), the following study procedures will also be performed:

- Approximately 72 mL of venous blood will be collected for cellular immunology assays.
- Approximately 20 mL of venous blood will be collected for antibody assays.
- Approximately 32 mL of venous blood will be collected for PBMC and plasma storage for secondary research.
- All SAEs/AESIs including PIMMCs/MAAEs/NOCMCs will be recorded on the appropriate DCF.

6.7 Early Termination Visit

- Interim medical history, including an assessment for new medical conditions will be obtained by interview of subjects and any changes since the previous clinic visit, phone call, or other form of contact will be noted.
- All concomitant medications will be recorded on the appropriate DCF.
- All AEs will be recorded on the appropriate DCF (if prior to Visit 09 for Stage 1, Groups 1 and 3A, Visit 12 for Stage 1, Groups 3B and 4, Visit 06 for Stage 2, Groups 5-7, 9-11, and 13-15, and Visit 12 for Stage 2, Groups 8 and 12).
- Memory Aid information will be reviewed with subjects (if within 7 days after the last study vaccination).

- Vital signs, including oral temperature, pulse, and BP, may be obtained if indicated. Subjects must not eat or drink anything hot or cold within 10 minutes prior to taking oral temperature.
- A targeted physical examination may be performed, if indicated, based on review of interim medical history, by a study clinician licensed to make medical diagnoses and listed on the Form FDA 1572 as the site PI or sub-investigator.
- Approximately 14 mL of venous blood will be collected for clinical safety labs (WBC, HgB, PLT, ALT, AST, ALP, Cr, CK, and T Bili) to be performed by the local clinical laboratory (if within 7 days after the last study vaccination).
- Approximately 80 mL of venous blood will be collected for cellular immunology assays.
- Approximately 20 mL of venous blood will be collected for antibody assays.
- Approximately 32 mL of venous blood will be collected for PBMC and plasma storage for secondary research.
- STAGE 1, Groups 3B and 4 and STAGE 2, Groups 5, 6, 7A, 7B, 8A, 8B, 9, 10A, 10B, 11A, 11B, 12A, 12B, and 13-15: Approximately 2.5 mL of venous blood will be collected for identification of transcriptomal signatures associated with vaccine reactogenicity and immunogenicity (if on or prior to Day 8 of either vaccination).
- STAGE 1, Groups 3B and 4 and STAGE 2, Groups 5, 6, 7A, 7B, 8A, 8B, 9, 10A, 10B, 11A, 11B, 12A, 12B, and 13-15: Approximately 4 mL of venous blood will be collected for cytokines (if on or prior to Day 8 of either vaccination).
- All SAEs/AESIs including PIMMCs/MAAEs/NOCMCs will be recorded on the appropriate DCF.

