5.2.4 Follow-up for Subjects that Discontinued Study Intervention

Discontinuation of study intervention does not require discontinuation from the study, and the remaining study procedures should be completed as indicated by the Schedule of Activities. If a clinically significant finding is identified, including, but not limited to, changes from baseline, after enrollment, the participating site PI or qualified designee will determine if any change in subject management is needed. Any new clinically relevant finding will be reported as an AE.

If the participant is enrolled and seeks vaccination with an EUA/licensed COVID-19 vaccine outside of the study, he/she will be encouraged to discuss this intention proactively with the study investigator and research team and will be able to receive the authorized vaccine at least

one month after the last study vaccination. An unscheduled visit will occur, if possible, prior to the receipt of an EUA/licensed COVID-19 vaccine. The remaining study procedures should be completed as indicated by the Schedule of Activities or the participant will only be followed for safety.

The data to be collected at the time of study intervention discontinuation should include the following:

- Clinical safety laboratory evaluations.
- Complete physical examination (PE).
- Vital signs (BP, pulse, and oral temperature).
- Immunogenicity evaluations.

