6.8 Unscheduled Study Visits

An Unscheduled Visit may occur at any time during this trial and will be conducted in clinic or at home, based on participating site and subject preference. Any of the following activities may be performed:

- Interim medical history, including an assessment for new medical conditions will be obtained by interview of subjects and any changes since the previous clinic visit, phone call, or other form of contact will be noted (if indicated).
- All concomitant medications will be recorded on the appropriate DCF.

- All AEs will be recorded on the appropriate DCF (if prior to Visit 09 for Stage 1, Groups 1 and 3A, Visit 12 for Stage 1, Groups 3B and 4, Visit 06 for Stage 2, Groups 5-7A, 7B, 9, 10A, 10B, 11A, 11B, and 13-15, and Visit 12 for Stage 2, Groups 8A, 8B and 12A, 12B).
- Memory Aid information will be reviewed with subjects (if within 7 days after the last study vaccination).
- Vital signs, including oral temperature, pulse, and BP, may be obtained if indicated. Subjects must not eat or drink anything hot or cold within 10 minutes prior to taking oral temperature.
- A targeted physical examination may be performed, if indicated, based on review of interim medical history, by a study clinician licensed to make medical diagnoses and listed on the Form FDA 1572 as the site PI or sub-investigator.
- Approximately 14 mL of venous blood will be collected for clinical safety labs (WBC, HgB, PLT, ALT, AST, ALP, Cr, CK, and T Bili) will be performed by the central (clinical) laboratory (if indicated).
- If a participant presents with signs or symptoms suggestive of pericarditis or myocarditis within 6 weeks post vaccination, blood will be collected for troponin-I or troponin-T testing and an electrocardiogram (ECG) will be performed.
- Approximately 80 mL of venous blood will be collected for cellular immunology assays.
- Approximately 20 mL of venous blood will be collected for antibody assays.
- Approximately 32 mL of venous blood will be collected for PBMC and plasma storage for secondary research.
- STAGE 1, Groups 3B and 4 and STAGE 2, Groups 5, 6, 7A, 7B, 8A, 8B, 9, 10A, 10B, 11A, 11B, 12A, 12B, and 13-15: Approximately 2.5 mL of venous blood will be collected for identification of transcriptomal signatures associated with vaccine reactogenicity and immunogenicity (if on or prior to Day 8 of either vaccination).

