Appendix G. VENIPUNCTURE VOLUMES – STAGE 2, GROUPS 5-7, 9-11, AND 13-15

Table 12: Stage 2 (Groups 5-7A*, 7B*, 9, 10A, 10B, 11A, 11B, and 13-15) Blood Volumes (mL)

Study Visit	V00	V01	V02	V04	V05	V06	V07	V08	V09
Study Day post Study Vaccination	Scr -30d to - 1d	D1	D2+1d	D8+2d	D15+2d	D29±3d	D85±3d	D181±14d	D366±14d
Safety Labs including WBC, HgB, PLT, ALT, AST, ALP, T Bili, CK, Cr, PT/PTT, Serum Pregnancy ²	16.7			14 ¹					
HIV, HBsAg, Anti-HCV	12								
SARS-CoV-2 Serology (N-specific)	2								
PBMCs for Immunology (T and B cell Assays)		80			80	80	80	80	80
Serum for Immunology (Antibody Assays)		20			20	20	20	20	20
PBMC and Plasma Storage for Secondary Research		32			32	32	32	32	32
Transcriptomal Signatures		2.5	2.5	2.5					
Cytokines		4	4	4					
Per Visit Blood Volume Total (mL)	30.7	138.5	6.5	20.5	132	132	132	132	132
Cumulative Blood Volume (mL) (prior 56 days)	30.7	169.2	175.7	196.2	328.2	460.2	264	132	132
Running Blood Volume Total (mL)	30.7	169.2	175.7	196.2	328.2	460.2	592.2	724.2	856.2

Blood volume limit is 550 mL over an 8-week period. If the volunteer agrees to the optional leukapheresis visit, then up to 10-20 mL of additional safety bloods may be drawn before/during the procedure.

¹ PT/PTT and Serum Pregnancy will not be done at these visits.

² WOCBP only

* After protocol version 9.0 was implemented, it was decided not to enroll subjects into Groups 7 and 8 because of competing priorities and predicted difficulties enrolling into these two groups.

Appendix H. VENIPUNCTURE VOLUMES – STAGE 2, GROUPS 8 AND 12

Table 13: Stage 2 (Groups 8A*, 8B*, 12A and 12B) Blood Volumes (mL)

Study Visit	V00	V01	V02	V04	V05	V06	V07	V08	V10	V11	V12	V13	V14	V15
Study Day post 1 st Study Vaccination	Scr -30d to -1d	D1	D2+1	D8+2d	D15+2d	D29±3d	D57±3d	D58+1d	D64+2d	D71+2d	D85±3d	D141±3d	D237±14d	D422±14d
Study Day post 2 nd Study Vaccination							D1	D2+1d	D8+2d	D15+2d	D29±3d	D85±3d	D181±14d	D366±14d
Safety Labs including WBC, HgB, PLT, ALT, AST, ALP, T Bili, CK, Cr, PT/PTT, Serum Pregnancy ²	16.7			14 ¹			14 ¹		14 ¹					
HIV, HBsAg, Anti-HCV	12													
SARS-CoV-2 Serology (N-specific)	2						2							
PBMCs for Immunology (T and B cell Assays)		72			72	72	72			72	72	72	72	72
Serum for Immunology (Antibody Assays)		20			20	20	20			20	20	20	20	20
PBMC and Plasma Storage for Secondary Research		32			24		24			32	32	32	32	32
Transcriptomal Signatures		2.5	2.5	2.5			2.5	2.5	2.5					
Cytokines		4	4	4			4	4	4					

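### The unconditional 132 mL early-termination draw in Section 6.7 takes a fully sampled single-boost subject past the protocol's own 550 mL eight-week limit if the subject leaves between V06 and about Day 56

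*Protocol*

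**What the plan says.** Section 6.7 (Early Termination Visit) lists three research draws with no condition attached: "Approximately 80 mL of venous blood will be collected for cellular immunology assays", "Approximately 20 mL of venous blood will be collected for antibody assays", and a further 32 mL for PBMC and plasma storage. In the same list the safety labs, transcriptomic and cytokine samples do carry timing conditions.

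Section 6.8 (Unscheduled Study Visits) lists the same amounts, for example "Approximately 32 mL of venous blood will be collected for PBMC and plasma storage for secondary research", but introduces its list with "Any of the following activities may be performed".

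Table 8 agrees with 6.7. In the Early Termination column, ELISpot, ICS, antibody and PBMC storage have a plain X, while safety labs are footnoted.

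Section 5.2.4 says "An unscheduled visit will occur, if possible, prior to the receipt of an EUA/licensed COVID-19 vaccine". An outside vaccine is allowed from one month after the last study vaccination.

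Appendix G (Table 12) and Appendix H (Table 13) have columns for scheduled visits only. The one extra draw in their footnotes is 10-20 mL for leukapheresis. Both carry the rule "Blood volume limit is 550 mL over an 8-week period".

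**The concern.** The limit protects subjects, and the tables exist to show that the schedule respects it. They leave out a draw as large as the biggest routine research draw. If the scheduled total already leaves less than 132 mL of room, a site that carries out 6.7 as written breaks the limit, and a site that keeps the limit deviates from 6.7. The people affected are those leaving the study early. For single-boost groups, the time from which 5.2.4 foresees an unscheduled visit before an outside vaccine opens at about the time the V06 draw is completed.

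**Working it through.** **Inputs (Table 12, single-boost groups).** The per-visit row reads "Per Visit Blood Volume Total (mL) 30.7 138.5 6.5 20.5 132 132": screening 30.7, Day 1 138.5, Day 2 6.5, Day 8 20.5, Day 15 132, Day 29 (V06) 132 mL. The limit is 550 mL in 56 days. The early-termination draw is 80 + 20 + 32 = 132 mL.

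**Reproducing the plan's figure.** 30.7 + 138.5 + 6.5 + 20.5 + 132 + 132 = 460.2 mL, which matches the table's "Cumulative Blood Volume (mL) (prior 56 days) 30.7 169.2 175.7 196.2 328.2 460.2". Without screening it is 460.2 − 30.7 = 429.5 mL. Room left after V06 is 550 − 460.2 = 89.8 mL, or 550 − 429.5 = 120.5 mL. Both are less than 132.

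**Adding one early-termination visit.**

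| Situation (all scheduled draws taken unless stated) | 56-day total, mL | Against 550 |
|---|---|---|
| After V06, screening in window | 460.2 + 132 = 592.2 | +42.2 |
| After V06, screening not in window | 429.5 + 132 = 561.5 | +11.5 |
| As above, Day 1 cellular draw 72 mL (Section 6.2.1 allows 72-80) | 561.5 − 8 = 553.5 | +3.5 |
| Before or instead of V06, screening counted | 328.2 + 132 = 460.2 | within |
| After V06, Day 15 draw missed, screening counted | 592.2 − 132 = 460.2 | within |
| Day 57, Day 1 draw counted | 561.5 | +11.5 |
| Day 57, Day 1 draw not counted | 561.5 − 138.5 = 423.0 | within |
| Day 58 onward | at most 423.0 | within |

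Day 57 turns on whether a draw exactly 56 days earlier counts, and the tables disagree. Table 12 at Day 85 gives 264 mL, which includes the Day 29 draw. Table 11 at Day 113 gives 445.5 mL, which leaves out the Day 57 draw (445.5 + 132 = 577.5 if counted). Hence the wording *up to about Day 56*.

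**Unscheduled visits, single boost.** If all 132 mL are taken after V06, the totals are the same. A full unscheduled draw on Days 9-28 followed by V06 also reaches 561.5 to 592.2 mL.

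**Group 12 (Table 13), early termination at nominal visit dates.**
- After Day 29: 396.2 + 132 = 528.2 mL.
- After Day 58 or Day 64: at most 373.5 + 132 = 505.5 mL.
- After Day 71: 381.5 + 132 = 513.5 mL.
- After Day 85: 138.5 + 6.5 + 20.5 + 124 + 124 = 413.5, and 413.5 + 132 = 545.5 mL.

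None exceeds 550 mL.

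**Group 12, full optional unscheduled draw between Days 29 and 85, then the scheduled Day 85 draw.** Table 13 prints 505.5 mL at Day 85, counting the Day 29 draw exactly 56 days earlier. 505.5 + 132 = 637.5 mL. If that boundary draw is not counted, the total is 505.5 − 92 + 132 = 545.5 mL.

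**The case against.** The limit is printed under every blood-volume table as a general rule, so a careful site could read it as overriding 6.7, and all that is missing is a cross-reference. All volumes are approximate, and the smallest excess is 3.5 mL. That bears on size, but it does not remove the conflict. Section 6.7 states its research draws as things that will be done, and it conditions other samples in the same list but not these. The one stated exception found is in Section 8.2.3, which stops large cellular draws in pregnancy.

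Four stronger readings are tempting, and the documents do not support them.

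- *Every single-boost subject seen after Day 29 goes over.* The excess needs both the Day 15 and V06 draws. V06 may fall on Days 26-32, and leaving before it, or instead of it, stays at or below 460.2 mL.
- *An unscheduled visit by itself breaks the limit.* Section 6.8 is permissive, and the visit in 5.2.4 is of this kind and is asked for only if possible.
- *The 14 mL of safety labs raises the early-termination total further.* Section 6.7 takes those labs only within 7 days of the last vaccination. Only an unscheduled visit where they are indicated could add them.
- *Early termination breaks the limit in Group 12.* At nominal dates the highest total is 545.5 mL.

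**Conclusion.** The point holds for Section 6.7 in single-boost groups. With all scheduled draws taken, early termination after V06 and up to about Day 56 gives 561.5 to 592.2 mL, about 2% to 8% above 550 mL (11.5/550 and 42.2/550). The upper figure needs the screening draw to lie within 56 days. Screening at Day -30 has already left the window by Day 29, and Section 6.1 lets existing results replace some screening tests. The lower figure falls to 553.5 mL if Day 1 used 72 mL, which is still over.

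Under Section 6.8 the same totals arise only when a site chooses to take the whole draw. In Group 12 the risk is limited to a full optional draw followed by scheduled ones, reaching 637.5 mL by the counting Table 13 uses at Day 85. The Group 12 result assumes nominal visit dates; visits moved within their windows could change some days.

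The excess is modest and the affected period short, but following one section of the protocol breaks a limit set in another. This should be corrected.

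**What to change.** State in both 6.7 and 6.8 that the research draws are reduced or omitted as needed so that the rolling 56-day total, including that visit and any scheduled draw that follows, stays within 550 mL. Add to the footnotes of Tables 12 and 13 that early-termination and unscheduled draws count toward the limit, and say there whether a draw exactly 56 days earlier is included. Which draws to reduce is for the sponsor to decide; the arithmetic shows only that the sections must be reconciled.

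The cost is a few lines of protocol text and a running total kept at the site. The downside is fewer stored cells from a small number of visits.
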